1 PROTOCOL SUMMARY

1.1 SYNOPSIS

Title: Adherence to novel foot mat technology for early detection of DFU.

Study Description:

Innovations toward the prevention of DFU are needed. Early detection of changes in the foot that predict the development of DFU could allow timely intervention to prevent the limb damage that occurs with advanced DFU.

Studies have demonstrated that increased temperature in the foot presage the development of DFU. Temperature changes can accurately be detected by home monitoring devices and predict impending ulceration. Here we will test the uptake of novel foot temperature monitoring technology for a future intervention study to determine if a home monitoring device could prevent the occurrence of severe DFU for our patients at MMC.

We will conduct a longitudinal study to determine the adherence to an FDA cleared device, Podimetrics, which has been tested in other populations and shown to 1) decrease the risk of severe DFU, and 2) decrease the utilization of health care resources in high risk patients with a history of DFU. For this study, we will identify and enroll patients who are high risk for DFU. They will be identified from the EMR. After informed consent, study subjects will receive the foot mat and obtain training remotely from Podimetrics, which provides a standardized training program. Study subjects briefly stand on the mat daily, and the temperature data automatically is sent for analysis to Podimetrics to interpret the information. The study subjects will be evaluated over a six-month period to measure their daily use of the technology. Secondary outcomes of this study include the occurrence of DFU and use of health care resources. Study subjects will be contacted every month by the study team to assess foot health. Study subjects will be instructed to contact the study team during the study period to inquire if they develop any changes in the foot such as the diagnosis of DFU or require a foot cast for offloading or have any concerns about their feet.

If patients have an increase in temperature, the study team will be contacted by Podimetrics. After a review of symptoms, a standard care protocol will be executed: offloading (decrease in weight bearing) will be recommended. In one study 68% of cases

resolved via offloading alone without an outpatient visit. Should the inflammation persist (increased temperature), despite off loading, an examination would be necessary to identify and resolve its cause. In this case the patient will be instructed to follow up with their physician.

Objectives:

Primary Objective:

1. Determine the adherence to the foot monitoring device over six months.

Secondary Objectives:

1. Determine the prevalence of ulcers as detected by the device.
2. Determine the use of the health care system.

Endpoints:

Study Population:

Adherence to daily monitoring, development of ulcers

The study cohort are derived from patients who are at highest risk to develop a DFU. They are patients who had a prior DFU within 24 months. Other criteria include: 1. have no active ulcer at the time of enrollment, 2. Presence of neuropathy, 3. ambulatory, and 4. provide informed consent.

Description of Sites/Facilities

The study will be conducted at one site Albert Einstein College of Medicine (AECOM) and its affiliated Montefiore Medical Center.

Enrolling Participants:

Description of Study:

Subjects will undergo observation for 6 months

Study Duration:

12 months

Participant Duration:

6 months

1.2 SCHEMA

A. Overall study design

1. *Subjects will be identified from the EMR: Adults that were treated for DFU within past 24 months, who presently have no active DFU at the time of study consent.*
2. *Consent and enrollment: we will approach patients via email if available, and/or phone call/phone text to learn about the study. Subjects can also be enrolled during routine clinic visit by study member.*
3. *Interested patients will be seen in the CTSA study clinic or enrolled in their care clinic (primary care, vascular, podiatry etc), if they fulfill criteria we will obtain informed consent.*
4. *For consented patients: baseline demographic data will be extracted from the EMR and case report filled out.*
5. *All study subjects receive the intervention and training from Podimetrics.*
6. *Study subjects will be instructed how to set up the mat and directed to step on the mat daily*
7. *If they do not step on the mat, they will be contacted by Podimetrics to reinforce use*

8. Increase in foot temperature (increase in 2.2°C over two consecutive uses between and of six contralaterally sites), a marker for early ulcer, will trigger a call to the study team to the study subject and the PI for management (SOP of elevated temperature management below).
9. All study subjects will be called each month to determine if any ulcer development or health care utilization.

[figure not shown]
[figure not shown]

Figure 1. Overall study protocol

B. Enrollment

1. Potential study subjects will be contacted by email, if no response will follow up with phone call. If by email they are interested to hear more about the study we will then follow up with description of study. Patients will also be recruited from outpatient clinics (podiatry, primary care, vascular, endocrine) by study team members.
2. For patients who are interested in the study we will obtain consent in a study clinic visit

(they will get reimbursed for travel to study clinic).

3. Study clinic: obtain informed consent, obtain history, examine feet, review enrollment criteria,

Figure 2. Enrollment protocol

[figure not shown]
C. Intervention

1. After informed consent at study clinic, we will provide the mat and standardized training (45 minutes by phone preferably within one week of receiving mat-this is the Activation or on boarding). Subjects step on mat daily and Podimetrics will receive and interpret daily data generated by the mat. A prescription for the Mat will be faxed to Podimetrics.

2. *Podimetrics will provide reinforcement in the case of four days of monitoring is missed. The nurse will remind the participant of the importance of daily use of the study device to identify foot inflammation that can lead to diabetic foot complications; to continue completing daily foot self-exams (this is standard of care); to always use diabetic shoes or other prescribed footwear, even indoors; and to immediately notify the clinic if they notice any concerning changes to their feet.*
3. *Participants will be instructed to discontinue use of the mat in certain circumstances, including incidence of new DFU, new infection, Charcot arthropathy flare, or when using an offloading device, such as a total contact cast or removable cast walker, that would prevent the participant from using the study device.*
4. *At end of study the mat is mailed back to Podimetrics (the box has a shipping label).*

D. Management of foot temperature elevation/risk management plan

1. *Podimetrics will contact patient, determine if patient notes any skin changes, pain, fever.*
2. *If clinically well, advise patient to decrease mobility by 50% (a “routine” temp elevation). If clinical symptoms (pain fever, discharge)(an “emergent” elevation) : see provider*
3. *Continued monitoring of temperature daily, call patient daily to review symptoms and Podimetric data. If persistent patient the study team will recommend that they present to their foot care provider.*
4. *Podimetrics will also contact the PI if there is a temperature elevation and discuss plan. The PI will also record this increase in temperature and follow up with Podimetrics for resolution or need for physician visit. Thus both Podimetrics and the PI are aware of the temperature change and will follow till resolution.*

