4.4 STRATEGIES FOR RECRUITMENT AND RETENTION

- *We will enroll up to 8 participants per month depending on the time within the study.*
- *Study team will call participants monthly to maintain contact and obtain interim history regarding development of new DFU.*

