7.2 PARTICIPANT DISCONTINUATION/WITHDRAWAL OR LOSS TO FOLLOW UP

Participants are free to withdraw from participation in the study at any time upon request.

An investigator may discontinue or withdraw a participant from the study for the following reasons:

- Significant non-compliance
- If any clinical adverse event (AE), laboratory abnormality, or other medical condition or situation occurs such that continued participation in the study would not be in the best interest of the participant.

- If the participant meets an exclusion criterion (either newly developed or not previously recognized) that precludes further study participation
- Loss to follow up will be if he or she cannot be reached by the study staff.

The reason for participant discontinuation or withdrawal from the study will be recorded on the Case Report Form (CRF). In the event a participant withdraws from the study or is lost to follow up, we will enroll an additional participant.

Figure 5. Image of foot monitoring device

References

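### Visit counts rest on a monthly phone call alone and DFU mainly on it; one end-of-study EMR review of everyone enrolled would make both secondary outcomes more complete

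*Combined protocol and SAP*

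**What the plan says.** Section 1.2, part A, item 9 gives the method for both secondary outcomes: "All study subjects will be called each month to determine if any ulcer development or health care utilization". Section 4.4 repeats the call, but for ulcers only: "Study team will call participants monthly to maintain contact and obtain interim history regarding development of new DFU". Item 9 is therefore the only readable statement of how visits are ascertained.

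The EMR is named for two tasks, both before follow-up:
- finding patients (section 1.2, part A, item 1): "Subjects will be identified from the EMR: Adults that were treated for DFU within past 24 months";
- baseline data (item 4): "baseline demographic data will be extracted from the EMR and case report filled out".

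Section 6 lists two secondary outcomes: the number of participants who develop a DFU, and total ER and outpatient visits. It gives no data source, denominator or rule for missing data for either. The Synopsis words the ulcer objective in terms of detection by the device, which in practice means the temperature-alert route.

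Section 7.2 defines loss: "Loss to follow up will be if he or she cannot be reached by the study staff". It also says that a participant who withdraws or is lost is replaced. Section 4.3 censors data from admission when a DFU leads to hospitalization.

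A DFU can come to light in other ways. In the Synopsis, "Study subjects will be instructed to contact the study team during the study period" about foot changes, including a DFU diagnosis. In section 1.2, part C, the device company makes contact after four missed days. In part D, on a temperature elevation, "The PI will also record this increase in temperature and follow up with Podimetrics for resolution or need for physician visit".

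**The concern.** The contact that defines retention is also the contact that measures the outcome. When a participant can no longer be reached, the planned source for visits is gone and the main source for DFU is gone with it. Replacement then tends to fill the final group with people who stay in touch.

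People who disengage or become ill may be harder to reach. If their DFU rate or health care use is higher, counts based on those who answer will be too low. Section 3.1 says these data are collected to inform larger trials, so an understated DFU rate or visit count would carry into that planning. Meanwhile the team already works with a record system at its own site that holds part of the missing information.

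**Working it through.** **The plan's own figure.** Section 6 plans for 20 completers and up to 40 enrolled. It states no dropout rate, so 40 cannot be derived independently. With enrolment = 20 / (1 − d), rounded up:
- d = 20%: 20 / 0.80 = 25
- d = 30%: 20 / 0.70 = 28.6, so 29
- d = 40%: 20 / 0.60 = 33.3, so 34
- d = 50%: 20 / 0.50 = 40

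The ceiling therefore allows for up to half of those enrolled not completing. It is a limit, not a forecast, and it also covers exclusions.

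**Sources for each outcome, side by side.**

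| Source in the readable text | Counts visits? | Can reveal a DFU? | Needs an engaged participant? |
|---|---|---|---|
| Monthly call (1.2 A item 9; 4.4) | Yes (item 9) | Yes | Yes |
| Participant contacts the team (1.1) | No | Yes | Yes |
| Re-engagement call after missed days (1.2 C) | No | Possibly | Must be reachable |
| Temperature-alert follow-up (1.2 D) | No | Yes | Needs mat use |
| Record of hospitalizations (4.3, 6) | No | If the DFU leads to admission | Source not stated |
| EMR during follow-up | Not planned in the readable text | Not planned in the readable text | No |

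The mat is also to be stopped on a new DFU, an infection or use of an offloading device (1.2 C), which closes the alert route from then on.

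**Bounds on the DFU proportion.** Assumptions: x = 3 DFUs among 20 completers (the documents give no expected rate), and outcomes wholly unknown for the other N − 20. Lower bound = x / N. Upper bound = (x + N − 20) / N.

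| Enrolled N | Unknown | Lower | Upper |
|---|---|---|---|
| 25 | 5 | 3/25 = 12% | 8/25 = 32% |
| 30 | 10 | 3/30 = 10% | 13/30 = 43% |
| 40 | 20 | 3/40 = 7.5% (8%) | 23/40 = 57.5% (58%) |

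**Bias in a completers-only figure.** The completers' rate is 3/20 = 15%. If those not reached have twice that rate (30%, assumed), the rate among all enrolled is:
- N = 25: (3 + 5 × 0.30) / 25 = 18%, so the completers' figure is 3 points too low
- N = 30: (3 + 10 × 0.30) / 30 = 20%, 5 points too low
- N = 40: (3 + 20 × 0.30) / 40 = 22.5%, 7.5 points too low

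If the two rates are equal, the bias is zero.

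**What record review could recover.** At N = 40 the bounds are 20/40 = 50 points apart. If EMR review settled the outcome for 50%, 80% or all of the 20 unknown (assumed), the width would fall to 10/40 = 25, 4/40 = 10 or 0 points.

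Visit totals have no natural upper limit, so the same bounds cannot be set. Each unreported visit lowers the total.

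**The case against.** The strongest reply has four parts.

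- **DFU is not known from the call alone.** Participant-initiated contact, re-engagement calls, alert follow-up and recorded hospitalizations can all reveal one. This stands. A reader might infer that both outcomes are missing for exactly those who stop answering; the documents do not support that for DFU. Most of these routes still need an engaged participant, however, and none counts ER or outpatient visits.
- **Absence of EMR follow-up is inferred from silence.** The content of the Schedule of Activities and the case report form were not available in readable form. A reader might conclude that the EMR is used only at baseline; the text supports only that no readable section plans later use. If later use is planned, section 6 should say so.
- **Non-completion is not the same as an unknown outcome.** A DFU reported before contact was lost is known. Section 7.2 allows withdrawal for newly meeting an exclusion criterion, and active DFU is one (section 4.2), so that participant's outcome is known. A reader might take 8% to 58% as the expected uncertainty. It is an arithmetic extreme at the enrolment ceiling, and its upper end needs all 20 non-completers to ulcerate.
- **These are secondary counts that section 6 says the study is not powered for.** This limits the weight of the point. It does not answer it, because low power concerns precision, while selective loss of outcomes can shift the estimate.

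**Conclusion.** The point holds in a limited form. In the readable text, visit counts rest solely on the monthly call and DFU rests mainly on it. Being unreachable is the definition of loss, and lost participants are replaced. The secondary counts may therefore be incomplete for disengaged participants and could understate DFU and health care use.

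The size is uncertain because no dropout or DFU rate is given. The bounds and the bias figures above rest on the assumed 3 of 20, and the bias figures also on an assumed doubling of risk. The actual loss should be smaller than the bounds suggest.

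The primary outcome is not touched, since mat use is transmitted automatically. No test or decision rule depends on the secondary counts. This is an inexpensive improvement to what the study can pass on to a later trial, not a flaw in its main result.

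**What to change.** State the data source for each secondary outcome in section 6, and add one end-of-study EMR review:

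- **Who:** every enrolled participant, including those withdrawn or unreachable, unless they decline record review.
- **What:** the listed secondary outcomes only, namely DFU, ER visits and outpatient visits, over the six-month observation period.
- **How combined:** keep the monthly call, count an event documented by either source, and count a visit found in both only once.
- **How reported:** use all enrolled as the denominator and give the number whose outcome remains unknown.
- **Reconcile:** say how the review window fits the section 4.3 rule that censors data from hospital admission, so that the two do not conflict.

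The cost is at most 40 chart reviews by a team that already uses this EMR, so some staff hours, and possibly a line in the consent form if record review is not already covered. Care received outside the site's system will still depend on the call, so the review reduces the gap without necessarily closing it.

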4.3 A STUDY SUBJECT DEVELOPS A DFU REQUIRING HOSPITALIZATION

1. Data is censored from the date of hospital admission.

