6 STATISTICAL CONSIDERATIONS

This study is primary to assess adherence to the monitoring device. It is not powered to assess clinical outcomes or use of health care resources.

- We will plan for 20 subjects to complete the study, and plan to enroll up to 40 patients to account for drop out or exclusion.
- Measurement of adherence (primary outcome)
 - Adherence is defined as > 3 days/week during the six month period
 - We will record the number of re-engagement calls per participant over the 6 month study period
 - We will record the number lost to follow up, unable to comply, or are hospitalized (4.2, 4.3)
- Measurement of secondary outcomes
 - Number of subjects who develop a DFU over the course of the study
 - Utilization of health care resource use (total number of: ER visits, outpatient visits) over the course of the study

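### The plan tells participants to stop using the mat in certain situations but does not say how those days count in the primary outcome, so following the instruction can be scored as non-adherence

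*Combined protocol and SAP*

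**What the plan says.** The primary objective (Section 1.1) is: "Determine the adherence to the foot monitoring device over six months". Section 6 makes it operational in one line: "Adherence is defined as > 3 days/week during the six month period". It does not say whether the threshold is an average or must be met every week, and it does not mention days on which use was not allowed.

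Section 1.2, part C, item 3 instructs non-use: "Participants will be instructed to discontinue use of the mat in certain circumstances, including incidence of new DFU, new infection, Charcot arthropathy flare". The same item adds a further reason, a cast or walker worn for offloading that makes standing on the mat impossible. No duration or restart rule accompanies this.

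Three other provisions bear on the point:

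- Section 4.3, headed "A STUDY SUBJECT DEVELOPS A DFU REQUIRING HOSPITALIZATION", has one rule: "Data is censored from the date of hospital admission".
- Section 7.2 lists reasons for which an investigator may withdraw a participant, among them: "If the participant meets an exclusion criterion (either newly developed or not previously recognized) that precludes further study participation". Active DFU is an exclusion criterion in Section 4.2. Participants who withdraw or are lost are replaced.
- Section 1.2, part C, item 2 sets the reminder: "Podimetrics will provide reinforcement in the case of four days of monitoring is missed". Part A, item 7 likewise provides for contact with anyone not using the mat. Neither makes an exception for a participant told to stop, and Section 6 records the number of re-engagement calls.

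**The concern.** Adherence is the only primary outcome, and the study is meant to inform larger trials. A measure of adherence should separate people who could use the mat and did not from people who were told not to. Read literally, Section 6 does not separate them.

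The treatment of similar events is also uneven. A new ulcer that leads to admission is censored from the admission date; a new ulcer managed as an outpatient is not addressed. Even for the admitted participant, days between the stop instruction and admission remain in the count. Infection, Charcot flare and offloading devices have no scoring rule unless they come with a DFU admission.

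The cohort is chosen for high ulcer risk and new DFU is a secondary outcome, so instructed stops are foreseeable. Any misclassification would fall on participants who develop foot problems. The reminder adds a second inconsistency: a participant following the stop instruction would, after four missed days, be due a call encouraging daily use, and that call would enter the re-engagement count.

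**Working it through.** The plan states no adherence target, precision or expected number of stops, so it has no figure of its own to reproduce on this point. The check is arithmetic on the Section 6 rule.

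**Inputs.** Threshold: more than 3 days/week (Section 6). Period: six months, taken as 26 weeks = 182 days. Completers: 20 (Section 6). Pause lengths and usage rates are assumptions, because the plan gives none.

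**Reading 1: every week must qualify.** A week with no use has 0 days, which is not above 3. One full week of instructed non-use makes the participant non-adherent, however diligent otherwise.

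**Reading 2: six-month average, off-days counted as non-use.**

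- 3 × 26 = 78, and the threshold is strict, so at least 79 use-days are needed.
- For a participant using the mat d days in each permitted week, weeks of use needed = 79/d and tolerable weeks off = 26 − 79/d.
- d = 7: 79/7 = 11.29, leaving 14.71 weeks off (182 − 79 = 103 days).
- d = 5: 79/5 = 15.80, leaving 10.20 weeks off.
- d = 4: 79/4 = 19.75, leaving 6.25 weeks off.

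Average scored for a pause of w weeks = d × (26 − w)/26:

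| Weeks off | d = 7 | d = 5 | d = 4 |
|---|---|---|---|
| 4 | 5.92 | 4.23 | 3.38 |
| 8 | 4.85 | 3.46 | 2.77 (fails) |
| 12 | 3.77 | 2.69 (fails) | 2.15 (fails) |
| 16 | 2.69 (fails) | 1.92 (fails) | 1.54 (fails) |

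**Permitted-days scoring.** Score = 7 × (use-days on permitted days)/(permitted days). For d = 4 with 8 weeks off, there are 4 × 18 = 72 use-days in 7 × 18 = 126 permitted days: 7 × 72/126 = 4.0 days/week, adherent. Over the full period the same person scores 72/26 = 2.77, non-adherent.

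**Effect on the estimate.** With 20 completers each reclassification moves the proportion by 1/20 = 5 percentage points. As an illustration, assume 16 of 20 are adherent while use is permitted: 80% (Clopper-Pearson 95% CI 56% to 94%). If 1, 2, 3 or 4 of those 16 are scored non-adherent because of an instructed stop, the estimate becomes 75%, 70%, 65% or 60%.

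**The case against.** The strongest reply is that Section 6 is silent, not contradictory: it nowhere says that instructed-off days count as missed. That is fair. A reader might infer that following the stop instruction automatically scores as non-adherence, and the documents do not support that. On the average reading a daily user can be off for 103 days and still qualify, so many temporary stops would change nothing. What stands is that the literal rule can produce this result and nothing in the plan prevents it.

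Second, Section 7.2 offers a way out: a participant with a new active DFU may be withdrawn and replaced, and up to 40 are enrolled to obtain 20 completers. It would be wrong to treat Section 4.3 as the only provision that could remove such a participant. But withdrawal is discretionary, the plan does not say how a withdrawn participant's adherence is scored, and the other stop reasons are not named exclusion criteria. Routine withdrawal would also replace misclassification with selection.

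Third, use over the whole six months, interruptions included, is a legitimate quantity for judging whether the technology could be deployed (Section 2.1). That stands, and is a reason to report both quantities. It is also true that a permitted-days score could call someone adherent after one good week before a stop, so a minimum is needed.

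Finally, the case report form is not reproduced in the documents, so stop dates may already be collected. That affects the cost of the fix, not the missing scoring rule.

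**Conclusion.** The point holds as a gap between stated rules: the plan instructs non-use in four situations, and the primary outcome has no rule for that time unless a DFU leads to admission. It should be fixed, but it is a clarification to a small single-arm study with no stated hypothesis test, and it can be made without changing conduct.

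Whether a given stop changes a participant's classification depends on the reading of the threshold, the length of the pause and the usual rate of use; the limits above assume a 26-week period and a constant rate on permitted days.

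Two stronger conclusions are tempting and are not supported. One is a share of the sample misclassified. Assuming that 20% to 30% stop at a uniform time and never resume, and using 78 days as the cut, gives 0.20 × (78/7)/26 = 8.6% to 0.30 × (78/4)/26 = 22.5%. The documents supply neither that incidence nor the absence of resumption, and the calculation ignores censoring under Section 4.3 and withdrawal under Section 7.2. The other is that the adherence figure cannot be interpreted at all; nothing in the documents shows that.

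**What to change.** In Section 6:

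- State whether the threshold is a six-month average or applies each week and, if weekly, how partly permitted weeks are scored.
- Score primary adherence over days on which mat use was permitted, taking documented instructed-stop days out of both numerator and denominator.
- Set in advance a minimum number of eligible days for a participant to be scored, and state how participants withdrawn under Section 7.2 are handled.
- Report eligible days per participant, and add a sensitivity analysis over all 182 days, which keeps the whole-period quantity.
- Report reminder calls made during instructed stops separately from other re-engagement calls.

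Record the stop and restart dates of each instructed stop, using the existing monthly call. Reconcile Section 1.2 (parts A and C) with Sections 4.3, 6 and 7.2, including the reminder and the stop instruction. This is a change to scoring and reporting only; it takes no view on when the mat should be stopped or restarted.

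The cost is a revised definition in Section 6 and, if not already collected, two date fields for each stop. The downside is that denominators will differ between participants, so those with few eligible days will have less precise scores.
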